5.5. Study Intervention Compliance

Study drug will be returned for accountability at Week 4, Week 8, and Week 12. The Investigator is responsible for ensuring that dosing is administered in compliance with the protocol.

5.6. Concomitant Therapy

Concomitant medication is any medication (including over-the-counter [OTC] medication, prescription medication, vaccines, vitamins, and supplements) that the subject is receiving at Screening or receives during the study. All concomitant medications must be recorded, along with:

- Reason for use
- Dates of administration, including start and end dates
- Dosage information, including dose and frequency

All concomitant medications should be compared against the list of prohibited medications and the list of other medications of concern provided in [Section 12.3](#). Subjects should be instructed to contact the site immediately any time a new medication is required during the course of the

study, including prescription and OTC medications, even those to be used for only a short period of time (eg, antibiotics, cold and flu remedies, gastrointestinal [GI] therapies, opioids or other pain relievers). The Medical Monitor should be contacted if there are any questions regarding concomitant or prior therapy.

5.6.1. Prohibited Concomitant Medications

- Use of other investigational drugs including GnRH agonists and antagonists, metformin and anti-androgens (spironolactone), as well as investigational devices are prohibited during the study
- Rosiglitazone, aromatase inhibitors, testosterone, growth hormones or any other medication or supplement that could impact subject safety or confound interpretation of study results are prohibited
- Moderate to strong inhibitors and/or inducers of CYP3A4; this includes consumption of grapefruit, grapefruit juice, or any foods that are known to be strong CYP3A4 inhibitors from 1 day before the first dose of study drug until after the final dose
- Sensitive substrates or narrow-therapeutic-range substrates of CYP3A4 (eg, oxycodone)
- Ethinyl estradiol >35 µg
- Sensitive substrates or narrow-therapeutic-range substrates of BCRP (except those that can be administered QD in the morning, separated by approximately 10 hours from evening administration of study drug)

[Appendix 12.3](#) provides a non-exhaustive list of medications, including many commonly used medications, that are prohibited because of their potential for metabolic interactions with tildacerfont. It is critical that each subject's concomitant medications are carefully compared to the list in [Appendix 12.3](#).

In all cases, if there is a question or concern about a specific medication being used by the subject, it is appropriate to review the usage with the Medical Monitor before enrolling the subject in the study and/or making a change in concomitant medications.

6. STUDY DRUG DISCONTINUATION AND PARTICIPANT WITHDRAWAL

6.1. Study Drug Discontinuation

Subjects may voluntarily discontinue study drug at any time. The Investigator and/or Sponsor may also discontinue a subject's study drug at any time. When feasible, Investigators should discuss any safety concerns with the Medical Monitor as soon as possible to determine whether a subject should continue or discontinue study drug. Study drug will be discontinued in subjects who experience individual treatment-stopping criteria described within this section. The Sponsor and Investigator will make efforts (when possible) to continue to collect data on subjects who discontinue study drug.

If study drug is discontinued, the Investigator will report the discontinuation to the Medical Monitor, document the date and reason for study drug discontinuation on the appropriate electronic case report form (eCRF), schedule an Early Termination Visit for the subject as soon as possible (see the Schedule of Activities in [Section 12.2](#)), provide or arrange for appropriate follow-up, and document the course of the subject's condition.

Subjects who prematurely discontinue study drug may be replaced at the discretion of the Sponsor to ensure adequate numbers of evaluable subjects.

6.1.1. Dose-Limiting Toxicity Stopping Criteria

A dose-limiting toxicity (DLT) is defined as a Common Terminology Criteria for Adverse Events (CTCAE) Grade 3 or higher treatment-emergent AE (TEAE) considered at least possibly related to study drug. If a subject experiences a DLT, study drug will be discontinued. DLTs are clinically significant AEs (see [Section 6.1.9](#)).

6.1.2. Safety Monitoring and Stopping Rules for Abnormal Liver Chemistry Measurements

The criteria in [Table 2](#) were adapted in accordance with the non-binding recommendations contained within the Food and Drug Administration (FDA) Guidance for Industry Drug-Induced Liver Injury: Pre-marketing Clinical Evaluation, from the U.S. Department of Health and Human Services in July 2009.

Although there is no reasonable expectation that study drug exposure of ≤ 200 mg QD will result in hepatic toxicity, out of an abundance of caution in this study, abnormal transaminase results will be assessed as follows.

If stopping criteria are met at any time during the Treatment Period, study drug should be held until confirmatory testing of the transaminase, with additional measurements of total bilirubin, alkaline phosphatase, complete blood count (CBC), and international normalized ratio (INR) is performed and be reported as an adverse event of special interest (AESI). Ideally, confirmatory testing would be performed within 48-72 hours of the initial receipt of the abnormal result. Confirmation testing through the central lab is preferred, but local laboratory testing may be necessary in certain circumstances. In cases where a possible Hy's Law case is present or any

other seriousness criteria are met, this should be reported as a SAE and AESI. [Table 2](#) outlines specific stopping criteria for this study.

Table 2. Stopping Criteria and Increased Monitoring for Liver Chemistry Elevations

Criteria	Actions
Appearance of fatigue, nausea, vomiting right upper quadrant pain or tenderness, fever, jaundice, rash and/or eosinophilia (>5%) believed to be related to liver injury or hypersensitivity.	Hold study drug, measure liver chemistry (AST/ALT/ALP), total bilirubin, total bile acids, CBC with differential and INR within 48-72 hours and notify Sponsor.
ALT or AST \geq 5x ULN	Discontinue study drug and notify Sponsor. Follow the protocol's Laboratory Monitoring of Liver Function .
ALT \geq 3x ULN	
Treatment Periods 1 and 2:
 
 
Monitor liver chemistry (AST/ALT/ALP), total bilirubin, total bile acids, CBC with differential and INR within 48-72 hours and notify Sponsor 
If no other stopping criteria are met, monitor AST/ALT/ALP and INR 2x weekly for the remainder of the current treatment period (may be performed weekly if AST/ALT stabilizes and the subject is asymptomatic) while continuing study drug 
If ALT $>3x$ ULN at the conclusion of the current treatment period, withdraw the subject from the study 
Treatment Period 3:
 
 
Follow the same notification and monitoring instructions detailed in (a) and (b) above for Treatment Periods 1 and 2. 
If ALT $>3x$ ULN persists for 4 weeks, discontinue study drug and notify Sponsor

Criteria	Actions	
ALT \geq 3x ULN	AND total bilirubin \geq 2x ULN (>35% direct bilirubin) ¹	Discontinue study drug and notify Sponsor. Possible Hy's Law case— report as SAE and AESI
	AND INR >1.5	Discontinue study drug and notify Sponsor. Possible Hy's Law case— report as SAE and AESI
	AND total bile acids $>3x$ ULN	Hold study drug and notify Sponsor. Measure liver chemistry (AST/ALT/ALP), total bilirubin, total bile acids, CBC with differential and INR within 48-72 hours and discuss with Medical Monitor whether to discontinue study drug.
	AND the appearance of fatigue, nausea, vomiting right upper quadrant pain or tenderness, jaundice, fever, rash and/or eosinophilia (>5%).	Discontinue study drug and notify Sponsor.

Abbreviations: AESI, adverse event of special interest; ALP, alkaline phosphatase; ALT, alanine aminotransferase; AST, aspartate aminotransferase; CBC, complete blood count; INR, international normalized ratio; SAE, serious adverse event; ULN, upper limit of normal.

¹ If serum bilirubin fractionation is not immediately available, discontinue study drug if ALT \geq 3x ULN and bilirubin \geq 2x ULN and record the presence/absence of detectable urinary bilirubin on dipstick, which is indicative of direct bilirubin elevations suggesting liver injury.

Investigation of the underlying cause of these transaminase elevations should include, but is not limited to:

- A detailed history of symptoms as well as current and prior medical diseases, especially biliary tract disease, co-morbid conditions associated with development of nonalcoholic steatohepatitis, and cardiovascular disease that would compromise adequate blood supply to the liver
- Examination of concomitant drug use (inclusive of OTC, herbal/dietary supplements, alcohol and recreational drug use)
- Environmental and chemical exposures
- Serology testing, as appropriate, based on laboratory findings, clinical exam and exposure history (ie, viral hepatitis, Epstein Barr virus)
- Additional investigations as appropriate such as GI/hepatology consultation, imaging studies or other laboratory testing may be performed at the discretion of the Investigator, in consultation with the Sponsor Medical Monitor.

Laboratory Monitoring of Liver Function:

- Monitor liver enzymes, total bilirubin, total bile acids and INR at least 2 times a week until transaminase levels are $<3x$ ULN, total bile acids are $<5x$ ULN, total bilirubin $<2x$ ULN and INR $\leq 1.5x$ ULN or levels stabilize, and the subject is asymptomatic.

- Obtain additional tests to evaluate liver function, such as fractionated bilirubin, as deemed appropriate.
- Thereafter, repeat testing will be performed as appropriate for the clinical circumstance until resolution or stability of transaminase values, total bilirubin, total bile acids and INR is achieved and any symptoms, if present, have abated.

In the event that study drug is discontinued, the decision to rechallenge will be made on a case-by-case basis and will require written approval by the Sponsor.

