3.1.2.4. Treatment Periods

Subjects will have 2 clinic visits in Treatment Period 1 (Weeks 1 and 4), and 1 clinic visit each in Treatment Periods 2 and 3 (Weeks 8 and 12, respectively).

At all clinic visits, including Day 1, concomitant medication and AE information will be reviewed. Vital signs and body weight will be measured. A pregnancy test, physical exam (either full or abbreviated), Columbia-Suicide Severity Rating Scale (C-SSRS), ECG, and 8 A.M. blood draw for PK will be conducted. Clinical laboratory and hormone assessments will be done, and A.M. serum cortisol will be collected. See [Section 12.4](#) for details of clinical laboratory and hormone assessments.

Telephone contacts will be conducted at Weeks 2, 6, 10 for Treatment Periods 1, 2, 3, respectively.

Study drug will be dispensed for the next treatment period at Weeks 4 and 8.

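### Table 2 keeps a subject with ALT ≥3x ULN on drug while repeating only AST/ALT/ALP and INR, so its own bilirubin, bile-acid and eosinophil criteria cannot be re-checked

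*Protocol*

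**What the plan says.** Protocol Section 6.1.2, Table 2 sets out three steps for ALT ≥3x ULN in Treatment Periods 1 and 2.

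- Item (a) is a single full recheck: "Monitor liver chemistry (AST/ALT/ALP), total bilirubin, total bile acids, CBC with differential and INR within 48-72 hours and notify Sponsor".
- Item (b) governs continued dosing: "If no other stopping criteria are met, monitor AST/ALT/ALP and INR 2x weekly for the remainder of the current treatment period". Testing may drop to weekly once AST/ALT are stable and the subject has no symptoms.
- Item (c) acts if ALT is still above 3x ULN when the period ends. The instruction is then, for the current "treatment period, withdraw the subject from the study".

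For Treatment Period 3 the table says: "Follow the same notification and monitoring instructions detailed in (a) and (b) above for Treatment Periods 1 and 2". Item (c) is replaced there by discontinuation if ALT stays above 3x ULN for 4 weeks.

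Four further rows combine ALT ≥3x ULN with a second finding:

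- total bilirubin ≥2x ULN with more than 35% direct (discontinue, possible Hy's Law);
- INR >1.5 (discontinue, possible Hy's Law);
- total bile acids >3x ULN (hold);
- listed symptoms and/or eosinophilia >5% (discontinue).

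The text before the table applies the criteria throughout dosing: "If stopping criteria are met at any time during the Treatment Period".

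After the table, the subsection Laboratory Monitoring of Liver Function gives another repeat panel: "Monitor liver enzymes, total bilirubin, total bile acids and INR at least 2 times a week until transaminase levels are" below 3x ULN, with limits for the other analytes, or until levels stabilise, with the subject asymptomatic. Table 2 refers to that subsection by name only in the ALT or AST ≥5x ULN row, where drug is discontinued: "Follow the protocol's Laboratory Monitoring of Liver Function".

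**The concern.** Item (b) makes continued dosing conditional on no other stopping criterion being met. After the one-off recheck, the repeat draws it orders cannot show whether that condition still holds for bilirubin, bile acids or eosinophils. The step-down to weekly testing has the same weakness, since it looks only at AST/ALT and symptoms.

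The subject at risk has ALT from 3x to below 5x ULN, no symptoms and INR ≤1.5, and attends a site that follows item (b) as written. If her bilirubin then rose to 2x ULN or more, nobody would see it until the next scheduled chemistry. The discontinuation and the expedited possible Hy's Law report would wait until then, with dosing continuing. Protocol Section 1.3 names hepatotoxicity as a potential risk.

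**Working it through.** **Panels side by side (Section 6.1.2)**

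| Analyte | Item (a), once | Item (b), repeated on drug | Laboratory Monitoring of Liver Function | Combination row that needs it |
|---|---|---|---|---|
| ALT | yes | yes | yes | all four |
| INR | yes | yes | yes | INR >1.5 |
| Total bilirubin | yes | no | yes | bilirubin ≥2x ULN |
| Total bile acids | yes | no | yes | bile acids >3x ULN |
| CBC differential | yes | no | no | eosinophilia >5% |

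The direct fraction is not listed in item (a) either. The table's footnote lets total bilirubin trigger discontinuation when fractionation is not immediately available, so total bilirubin is the analyte that matters.

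On item (b) draws, 1 of the 4 rows is fully evaluable (INR), 1 is evaluable on clinical signs but not on eosinophils, and 2 are not evaluable (bilirubin, bile acids). Item (b)'s short list cannot be read as including bilirubin: wherever else Section 6.1.2 asks for bilirubin alongside the enzymes, it names it separately.

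**Length of the gap, if only item (b) is followed**

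Inputs:
- After Day 1, scheduled on-treatment chemistry falls on Days 28, 56 and 84 (Protocol Section 12.2).
- The item (a) recheck comes 2-3 days after the result.
- The next period's drug is handed out at the same visit: "Study drug will be dispensed for the next treatment period at Weeks 4 and 8".
- Samples go to a central laboratory (Protocol Section 7.1.5). Time to result is not given; I assume 1-3 days.

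Gap = day of next scheduled chemistry − day of item (a) panel.

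*Case 1.* ALT ≥3x ULN on the Day 28 sample, which is taken to belong to the period just ending. If ALT is above 3x ULN, item (c) withdraws her. Gap = 0 days.

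*Case 2.* Same sample, but the current period is taken to be the one in which the result arrives.
- Result: Day 28 + 1 to 3 = Day 29-31.
- Item (a) panel: + 2 to 3 days = Day 31-34.
- Gap to Day 56: 56 − 34 = 22 to 56 − 31 = 25 days, or 22/7 = 3.1 to 25/7 = 3.6 weeks.
- Draws without these analytes: 22/3.5 = 6.3 to 25/3.5 = 7.1, so 6-7 if twice weekly, or 3 if weekly.
- A Day 56 sample on the same reading: panel on Day 59-62, and 84 − 62 = 22 to 84 − 59 = 25 days. This is at 200 mg, where item (c) does not apply.
- Sensitivity to turnaround: with 0 days the panel is on Day 30-31 and the gap is 25-26 days; with 5 days it is on Day 35-36 and the gap is 20-21 days.

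*Case 3.* An unscheduled result received mid-period, for example on Day 42.
- Item (a) panel: Day 44-45.
- Gap to Day 56: 56 − 45 = 11 to 56 − 44 = 12 days.
- Draws: 11/3.5 = 3.1 to 12/3.5 = 3.4, so 3 if twice weekly.
- This does not depend on how the current period is read, because item (c) acts only at period end.

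If the site also follows Laboratory Monitoring of Liver Function, bilirubin and bile acids are covered and only the differential is missing.

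**The case against.** The best reply is that Laboratory Monitoring of Liver Function already covers this subject. It sits in the same section, its end-point is transaminases below 3x ULN, nothing in it restricts it to subjects off drug, and the paragraph on discontinuation that follows treats that as a separate event. Its panel contains item (b)'s, so a site can satisfy both. On that view the defect is a missing cross-reference.

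This stands in part. The broad reading is reasonable, and the two panels are compatible in the sense that one is wider. But the row that keeps the subject on drug states the narrower list and does not point to the wider one, while the ≥5x ULN row does. On the narrow reading, a subject still being dosed is tested for fewer analytes than one taken off drug. On the broad reading, two different repeat panels apply to the same subject. Neither includes the differential.

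The gap also depends on circumstances. Whether it is 0 or 22-25 days for a scheduled sample turns on a reading of the current period that the protocol does not settle. Case 3 needs an unscheduled draw, since Day 42 is a telephone contact. There is a route to one: Section 7.1.5 has clinically significant laboratory values repeated at least weekly, so an ALT below 3x ULN at Week 4 could cross the threshold mid-period.

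There are real safeguards. Item (a) requires a clear full panel and Sponsor notification first. Symptoms thought to be liver-related trigger a hold and a full panel. INR stays on the repeat list. Section 12.4 groups bilirubin and bile acids with the enzymes under clinical chemistry, so a laboratory might run them anyway, although the documents do not say so. None of these guarantees that an asymptomatic rise between visits is found. The eosinophil point is the weakest part, being one item in a mainly clinical list.

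Exposure is small. Section 1.3 reports transaminase rises at 400 and 1000 mg QD without bilirubin elevation, the planned tildacerfont group is 26 (Section 8.1), and SAP Section 15 records early discontinuation for business reasons. This limits how much the defect matters; it does not make the table consistent.

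**Conclusion.** The concern holds. While dosing continues at ALT ≥3x ULN, item (b)'s repeat panel cannot detect the bilirubin limb of possible Hy's Law, the bile-acid hold or the eosinophilia criterion. The INR limb and clinical symptoms remain detectable.

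At a site that follows item (b) alone, the time without bilirubin or bile acids ranges from 0 to 25 days across the three cases. The upper figure rests on the assumed 1-3 day turnaround and on managing a Day 28 or Day 56 result in the following period. Few subjects would be affected, but the rule concerns a named safety risk and the correction is cheap, so it should be made.

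**What to change.** In Table 2, item (b), make the repeat panel AST/ALT/ALP, total bilirubin (fractionated if raised), total bile acids, CBC with differential, and INR. Alternatively, have the ALT ≥3x ULN row cite Laboratory Monitoring of Liver Function and add the CBC differential to that subsection. Either way, state that this one panel governs while dosing continues in all three treatment periods. Thresholds and testing intervals stay as they are.

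The cost is one line of text and a few extra assays at blood draws already required, for the few subjects with ALT ≥3x ULN who stay on drug.

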3.1.2.5. Follow-up Visit

All subjects will return to the clinic (or, at the discretion of the Investigator, be contacted via telephone) for a final Follow-up Visit within 30 days after the last dose of study drug. Concomitant medication and AE information will be reviewed.

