3.1.2.6. Early Termination Visit

Subjects who received any dose of study drug and discontinue study drug early or withdraw from the study will undergo an Early Termination Visit as soon as possible after the last dose of study drug. The Investigator will inquire about the reason for withdrawal and request the return of all unused study drug. Early termination assessments will occur as outlined in the Schedule of Activities ([Section 12.2](#)).

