6.1.8. Platelet Stopping Criteria

- Platelet counts $<75,000/\mu\text{L}$ (Grade 3) should be confirmed with repeat laboratory testing within 72 hours of receipt of the initial test results.
- Platelet counts $<75,000/\mu\text{L}$ should be monitored every 48 to 72 hours; if they decrease below $50,000 \text{ mm}^3$, fail to normalize after 7 days, or clinical complications of thrombocytopenia develop, drug should be discontinued immediately, and the subject withdrawn from the study.
- Platelet counts $<50,000/\mu\text{L}$ should retest as soon as possible and discontinue drug immediately with withdrawal of the subject if testing is confirmatory.

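### The protocol does not keep subjects who stop drug in the visit schedule, and one liver rule and the platelet rule order withdrawal, so Week 12 DHEAS for the treatment-policy estimand can be lost (minor)

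*Protocol*

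**What the plan says.** **Estimand and analysis.** SAP 13.1.1 labels the primary estimand treatment policy, sets the variable as log-transformed change in DHEAS at Week 12, and disregards treatment interruption and discontinuation. SAP 13.1.3.1 places the formal test in the Week 12 ANCOVA. SAP 10.3 and 13.1.3.2 impute no missing DHEAS.

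**After drug is stopped.** Protocol 6.1 promises this much: "The Sponsor and Investigator will make efforts (when possible) to continue to collect data on subjects who discontinue study drug". Under 3.1.2.6, treated subjects who "discontinue study drug early or withdraw from the study will undergo an Early Termination Visit as soon as possible after the last dose". Section 6.1.6 likewise pairs permanent discontinuation for adrenal insufficiency with an Early Termination Visit. No section tells an off-drug subject to attend the remaining Week 8 or Week 12 visit.

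**Rules that order withdrawal.** Table 2 (6.1.2), item (c) for ALT at or above 3x ULN in Periods 1 and 2, applies when ALT remains above 3x ULN at period end: "treatment period, withdraw the subject from the study". Section 6.1.8 says "drug should be discontinued immediately, and the subject withdrawn from the study" and, for counts below 50,000, "discontinue drug immediately with withdrawal of the subject if testing is confirmatory".

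**Rules that only stop drug.** The rows for ALT or AST at or above 5x ULN, and for ALT at or above 3x ULN with raised bilirubin or INR, say "Discontinue study drug and notify Sponsor". The Period 3 counterpart of item (c) also stops drug only.

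**The concern.** A treatment-policy estimand asks what happens to DHEAS at Week 12 whether or not the subject is still on drug, so it needs a measurement after drug is stopped. The protocol leaves that measurement to best effort for all who stop, and for two laboratory findings it removes the subject from the study.

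Such a subject with a Week 4 DHEAS is in the mITT set but drops out of the Week 12 ANCOVA, for a reason that may be related to treatment. The ANCOVA would then describe those who stayed on drug, which is not the stated estimand. The withdrawal order is also hard to explain on safety grounds, since worse liver findings are managed by stopping drug and monitoring.

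**Working it through.** **1. Can a scheduled contact supply a Week 12 value?** SAP Table 4 windows: Week 8 is Days 44–71; Week 12 is Days 72–100 (target Day 85). Follow-up is at last dose + 30 days (protocol 12.2).

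- *Stop at Week 4:* last dose Day 27–28; 27 + 30 = 57 and 28 + 30 = 58. This is in the Week 8 window, before Day 72. Section 3.1.2.5 says within 30 days, which can only make it earlier. A last dose as late as Day 41 still gives Day 71. No scheduled contact reaches the Week 12 window.
- *Stop at Week 8:* last dose Day 55–56; follow-up at Day 85–86, inside the window. A value exists only if the contact is in clinic, on Day 72 or later, and DHEAS is drawn.

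**2. Is DHEAS drawn at that follow-up?**

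- *For:* the protocol synopsis has DHEAS at every clinic visit and lists the 30-day follow-up among clinic visits. Its efficacy summary says every visit. SAP 5 says visits in the follow-up period include efficacy assessments. SAP 9.4 would take the closest sample in the window if the scheduled visit is absent.
- *Against:* subjects return "for a final Follow-up Visit within 30 days after the last dose of study drug. Concomitant medication and AE information will be reviewed", with no hormone sample named. The contact may be by telephone (3.1.2, 12.2). SAP 5.2.2.1 and SAP Table 7 place hormones at Day 1 and Weeks 4, 8 and 12 only. SAP Table 4 also labels last dose +1 to +30 as Follow-up.

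The hormone row of protocol 12.2 is broken in the text available to me, so I do not rely on it.

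**3. The plan's own sample size.** Difference 164, SD 154, two-sided alpha 0.05, 2:1: the normal approximation gives 11 + 22 = 33 with 82.2% power (noncentral t 79.8%). 33 / 0.85 = 38.8, so N = 39 (26:13). The stated figures reproduce.

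**4. Power if active subjects lack a Week 12 value.**

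| Active : placebo | Normal approximation | Noncentral t |
|---|---|---|
| 22 : 11 | 82.2% | 79.8% |
| 21 : 11 | 81.6% | 79.1% |
| 20 : 11 | 81.0% | 78.3% |
| 19 : 11 | 80.3% | 77.4% |

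With no other dropout, 26:13 to 25:13 goes from 86.3% to 85.8% (noncentral t). The dropout allowance is 39 − 33 = 6 subjects, 4 of them active.

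**5. How often.** No event rate is given. At an assumed risk p per active subject, the chance of no case is (1 − p)^26: 88% at 0.5%, 77% at 1%, 59% at 2%, 35% at 4%.

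**6. Bias on the planned log scale.** Let L be the log effect in subjects who stay on drug, k the active subjects left out of n, and f the share of effect kept off drug (assumed). The treatment-policy effect is L × (1 − k(1 − f)/n).

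- k = 1, n = 22: smaller than reported by 4.5% (f = 0), 2.3% (f = 0.5), 0 (f = 1).
- k = 1, n = 26: 3.8%, 1.9%, 0.
- k = 2, n = 22, f = 0: 2/22 = 9.1%.

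Off-drug time by Week 12, using the 60-hour half-life in protocol 1.2.2, is 56 × 24 / 60 = 22.4 half-lives after a Week 4 stop and 28 × 24 / 60 = 11.2 after a Week 8 stop. Drug would be gone, so f = 0 is a reasonable extreme.

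Illustration with k = 1, n = 22, f = 0, no placebo change and an assumed baseline B, where L = ln((B − 164)/B):

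| B (mcg/dL) | Reported reduction | Treatment policy |
|---|---|---|
| 295 (lower ULN for eligible ages) | 55.6% | 53.9% |
| 450 | 36.4% | 35.1% |
| 650 (exclusion limit) | 25.2% | 24.2% |

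**The case against.** The strongest reply is that the two withdrawal rules are not the main cause. A subject stopped at Week 4 for ALT at or above 5x ULN also goes to an Early Termination Visit and has no scheduled Week 12 draw. That stands: replacing the word withdraw alone would not secure the data. A reader might blame Table 2 and 6.1.8 for the whole gap, but 3.1.2.6, 6.1 and 6.1.6 show that it covers every early stop. The two rules remove even the best-effort promise, which covers only those who discontinue drug.

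A reader might also infer that a Week 8 stop loses the Week 12 value, or probably does. The texts set out in step 2 of the working do not support that. They conflict, and no more can be said.

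A third tempting inference is that 6.1.9 limits liver cases on active drug to two. It does not: the study stops once a third drug-related AESI has occurred, and platelet events are not among the AESIs in 7.2.8.

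Finally, the practical stake is small. The protocol states that "there is no reasonable expectation that study drug exposure of" 200 mg QD or less will cause hepatic toxicity. SAP 13.1.1 assumes no clinically relevant intercurrent events, and SAP 10.6 calls the study exploratory. The MMRM keeps Week 4 and Week 8 values under missing-at-random. SAP 13.2 already counts discontinuers as non-responders. Sections 6.1 and 6.2 allow replacement, though that restores numbers and not the missing value. SAP 15 reports that the study ended early, so new wording has limited use here, while the smaller n would raise the 1/n share. All of this stands and sets the severity.

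**Conclusion.** The point holds as a minor one. The SAP declares an estimand that needs off-drug Week 12 DHEAS, and the protocol does not provide for collecting it. After a Week 4 stop or withdrawal, no scheduled contact can supply the value; after a Week 8 stop, the documents disagree. Item (c) and the platelet rule go further than the more severe liver rows by ordering withdrawal.

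At planned size, one affected active subject costs 0.5 to 0.7 point of power and makes the treatment-policy log effect 0 to 4.5% smaller than reported. With a baseline of 450 mcg/dL that is at most 36.4% − 35.1% = 1.3 percentage points. These sizes rest on an assumed event risk, baseline and off-drug reversal; no event at all is a realistic outcome. Nothing here supports a claim of material bias or lost power.

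**What to change.** Make the main change in protocol 6.1. Suggested text: *Subjects who stop study drug for any reason remain in the study and attend the remaining Week 4, 8 and 12 visits in clinic for DHEAS and safety, unless they withdraw consent, become pregnant, or continued visits are unsafe.*

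Then align the two rules. In Table 2 item (c) and in both withdrawal bullets of 6.1.8, replace withdrawal from the study with discontinuation of study drug. Leave thresholds, laboratory monitoring and withdrawal for pregnancy as they are. Section 6.2 needs no change, because it already ties withdrawal for a laboratory abnormality to the subject's best interest.

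The cost is wording in three places, plus two off-drug clinic visits after a Week 4 stop or one after a Week 8 stop, per affected subject. No safety rule is loosened.
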